## 1 INTRODUCTION AND OBJECTIVES OF ANALYSIS

This document presents the statistical analysis plan (SAP) for Protocol BHV3500-302 (C5301006): A Phase 2/3 Randomized, Double-Blind, Placebo-Controlled Study to Evaluate the Efficacy and Safety of Oral Zavegepant in Migraine Prevention.

This SAP contains the analysis details and methodology to answer the study objectives, including planned tables, listings, and figures (TLFs), which provide the basis for the results section of the clinical study report (CSR).

This SAP also references the Rimegepant/Zavegepant Core SAP, which is hereafter referred to as the "Core SAP".

Note that the study was terminated prematurely in December 2023 for business reasons and not a safety concern. As a result, the SAP is being amended from Version 7 to 8 to reduce the number of TLFs for the CSR in order to focus only on the most relevant objectives.

## 1.1 Research Hypothesis

Zavegepant 100 mg or zavegepant 200 mg soft gelatin capsule (SGC) oral dose taken daily is safe and effective for the prevention of migraine.

## 1.2 Schedule of Analyses

There is 1 planned database lock, last subject last visit (LSLV) database lock, which occurs when the last subject completes the Follow-Up Week 8 Visit. The LSLV final CSR is produced after the LSLV database lock.

No interim analyses are planned.

### 2 STUDY DESCRIPTION

### 2.1 Study Design

The study has 4 phases:

- Observation Phase (OP): Lasts approximately 28 days. Includes the Screening Visit and Prerandomization Laboratory Visit which must occur within 96 hours of the Baseline Visit.
- Double-blind Treatment (DBT) Phase:
  - o Includes the Baseline Visit at which randomization occurs, and Week 2, Week 4, Week 8, Week 12, and End of Treatment (EOT) Visits.
    - Subjects are randomized to 2:2:1:1 to zavegepant 100 mg, zavegepant 200 mg, placebo matching zavegepant 100 mg, or placebo matching zavegepant 200 mg.
    - Randomization is stratified by stable prophylactic migraine medication use through randomization (yes or no).

- o All randomized subjects who discontinue early from the DBT Phase should complete the EOT Visit. Otherwise, subjects should complete the Week 12 Visit.
- O Subjects are instructed to follow one of the following 2 dosing regimens:
  - Take four (4) 25 mg SGCs of blinded study drug every calendar day, if randomized to the zavegepant 100 mg or placebo matching zavegepant 100 mg treatment group
  - Take eight (8) 25 mg SGCs of blinded study drug every calendar day, if randomized to the zavegepant 200 mg or placebo matching zavegepant 200 mg treatment group.
- Open-label Extension (OLE) Phase:
  - Subjects who (1) complete the DBT Phase, (2) continue to meet all inclusion/exclusion criteria, and (3) have been compliant with the eDiary may enter the OLE Phase, pending review of Week 12 laboratory test results.
  - O Subjects are instructed to follow one of the following 2 dosing regimens:
    - Take four (4) 25 mg SGCs of OL zavegepant every calendar day, if randomized to the zavegepant 100 mg or placebo matching zavegepant 100 mg treatment group in the DBT Phase
    - Take eight (8) 25 mg SGCs of OL zavegepant every calendar day, if randomized to the zavegepant 200 mg or placebo matching zavegepant 200 mg treatment group in the DBT Phase.
  - Lasts up to 52 weeks, and includes the Week 14, Week 16, Week 20, Week 24, Week 28, Week 32, Week 36, Week 40, Week 44, Week 48, Week 52, Week 56, Week 60, Week 64, and EOT Visits.
  - All randomized subjects who discontinue early from the OLE Phase should complete the EOT Visit. Otherwise, subjects should complete the Week 64 Visit.

### Follow-up Phase

- Lasts up to 8 weeks, and includes Follow-up Week 2 and Follow-up Week 8 Visits primarily for safety assessments. These visits should occur approximately 2 weeks and 8 weeks, respectively, after the last visit in the last treatment phase (i.e., Week 12/EOT Visit if the subject did not enter the OLE Phase; Week 64/EOT Visit if the subject entered the OLE Phase).
- All randomized subjects should complete both follow-up visits, regardless of completing either treatment phase.

The design of the study is shown in Figure 1 and Figure 2. Approximately 2900 subjects are enrolled in order to randomize approximately 1440 subjects.

Figure 1 Study Schematic: Observation, DBT, and Follow-up Phases

[figure not shown]
[figure not shown]

Figure 2 Study Schematic: OLE and Follow-up Phases

# 2.2 Treatment Assignment

The Interactive Web Response System (IWRS) assigns a subject identifier number at the Screening Visit.

The IWRS randomizes eligible subjects to a treatment group (see Section 2.1) using permuted blocks of size 12 at the Baseline Visit. Randomization is stratified by stable prophylactic migraine medication use through randomization (yes or no).

The IWRS also assigns specific container numbers for study drug to be dispensed at the Baseline Visit and subsequent visits in the DBT and OLE Phases.

# 2.3 Blinding and Unblinding

This study is blinded to study drug active status (zavegepant versus placebo), but not to the dose level (100 or 200 mg), through the LSLV database lock (see Section 1.2). Draft TLFs for the LSLV final CSR are produced with dummy treatment groups prior to the LSLV database lock. TLFs for the LSLV final CSR are produced unblinded.

#### 2.4 Protocol and Protocol Amendments

BHV3500-302 SAP Versions 1 and 2 are based on BHV3500-302 Protocol Version 4 (28-Jun-2021).

BHV3500-302 SAP Versions 3 and 4 are based on BHV3500-302 Protocol Version 5 (16-Nov-2021), which added the OLE Phase and 2 exploratory objectives.

BHV3500-302 SAP Versions 5, 6, 7, 8, and 9 are based on BHV3500-302 Protocol Version 6 (16-May-2022), which modified the language in efficacy objectives and endpoints (i.e., changed "baseline" to "the OP") and added 1 exploratory objective.

### 3 STUDY OBJECTIVES AND ESTIMANDS

## 3.1 Objectives

A month is defined as 4 weeks (28 days) for the purpose of this protocol.

## 3.1.1 Primary Objective

To compare the efficacy of zavegepant to placebo as a preventive treatment for chronic migraine, as measured by the mean reduction from the OP in the number of migraine days per month over the entire DBT Phase.

# 3.1.2 Secondary Objectives

- 1. To compare zavegepant to placebo on the proportion of subjects with ≥ 50% reduction from the OP in the number of moderate to severe migraine days per month over the entire DBT Phase.
- 2. To compare the efficacy of zavegepant to placebo on the mean reduction from the OP in the number of migraine days per month in the last 4 weeks of the DBT Phase.
- 3. To compare the efficacy of zavegepant to placebo on the mean reduction from the OP in the number of migraine days per month in the first 4 weeks of the DBT Phase.
- 4. To compare the efficacy of zavegepant to placebo on the mean number of acute migraine-specific medication days per month over the entire DBT Phase.
- 5. To compare the mean change from baseline in the Migraine-Specific Quality-of-Life Questionnaire v 2.1 (MSQ) restrictive role function domain score at Week 12 of the DBT Phase between zavegepant and placebo.

- 6. To compare the mean change from baseline in the Migraine Disability Assessment (MIDAS) total score at Week 12 of the DBT Phase between zavegepant and placebo.
- 7. To evaluate the safety and tolerability of zavegepant during the DBT and OLE Phases.
- 8. To evaluate the frequency of alanine aminotransferase (ALT) or aspartate aminotransferase (AST) > 3x upper limit of normal (ULN) concurrent with total bilirubin (TBL) > 2x ULN in subjects treated with zavegepant during the DBT and OLE Phases.
- 9. To evaluate the frequencies of hepatic-related adverse events (AEs) and hepatic-related AEs leading to study drug discontinuation in subjects treated with zavegepant during the DBT and OLE Phases.

# 3.1.3 Exploratory Objectives

- 1. To compare the efficacy of zavegepant to placebo on the mean reduction from the OP in the number of migraine days per month and number of headache days per month by pain intensity (total; moderate or severe) in each month and over the entire DBT Phase.
- 2. To compare the efficacy of zavegepant to placebo on the proportions of subjects with  $\geq 50\%$  reduction,  $\geq 75\%$  reduction, and 100% reduction from the OP in the number of migraine days per month and number of headache days per month by pain intensity (total; moderate or severe) in each month and over the entire DBT Phase.
- 3. To compare the efficacy of zavegepant to placebo on the mean reduction from the OP in the number of migraine days per week and number of headache days per week by pain intensity (total; moderate or severe) in each of the first 4 weeks of the DBT Phase.
- 4. To compare the efficacy of zavegepant to placebo on the proportion of subjects with ≥ 50% reduction from the OP in the number of migraine days per week and number of headache days per week by pain intensity (total; moderate or severe) in each week of the first 4 weeks of the DBT Phase.
- 5. To compare the efficacy of zavegepant to placebo on the proportions of subjects with a migraine day and headache day by pain intensity (total; moderate or severe) on each day of the first week of the DBT Phase.
- 6. To compare the efficacy of zavegepant to placebo on the mean number of acute migraine-specific medication days per month in each month and over the entire DBT Phase.
- 7. To compare the efficacy of zavegepant to placebo on the mean number of acute migraine medication days per month in each month and over the entire DBT Phase.
- 8. To evaluate the frequency of liver function test (LFT) elevations (AST, ALT, or TBL) based on fold changes above ULN in subjects treated with zavegepant during the DBT and OLE Phases.
- 9. To evaluate the frequency of ALT or AST elevations > 3x ULN in temporal association with nausea, vomiting, anorexia, abdominal pain or fatigue in subjects treated with zavegepant during the DBT and OLE Phases.

- 10. To compare the mean changes from baseline in the MSQ preventive role function and emotional function domain scores at Week 12 of the DBT Phase between zavegepant and placebo.
- 11. To compare the mean changes from baseline in the MIDAS absenteeism and presenteeism scores at Week 12 of the DBT Phase between zavegepant and placebo.
- 12. To evaluate the mean changes from baseline in MSQ domain scores and MIDAS scores during the OLE Phase.
- 13. To evaluate the Preference of Medication (PoM) scale during the DBT and OLE Phases.
- 14. To evaluate the Satisfaction with Medication (SM) scale during the DBT and OLE Phases.
- 15. To evaluate the Clinical Global Impression change (CGI-c) scale during the DBT and OLE Phases.
- 16. To evaluate the pharmacokinetics of zavegepant 100 mg and 200 mg.

#### 3.2 Estimands

An estimand is the target of estimation to address the scientific question of interest posed by a study objective. The 4 attributes of an estimand include the population of interest, endpoint of interest, summary of the endpoint, and specification of how intercurrent events are reflected in the scientific question of interest.

For all objectives, the population of interest is defined through appropriate inclusion/exclusion criteria to reflect the targeted patient population for approval. Refer to the protocol for inclusion/exclusion criteria.

For efficacy and outcomes research endpoints, treatment group comparisons are based on zavegepant 100 mg verses placebo pooled and zavegepant 200 mg verses placebo pooled.

#### **Intercurrent Events**

Intercurrent events are those that occur after treatment initiation and either preclude observation of the endpoint or affect its interpretation.

Study drug discontinuation before the time point of interest defining the endpoint is considered an intercurrent event.

• For efficacy objectives assessed with a continuous endpoint during the DBT Phase, study drug discontinuation is handled with a "hypothetical strategy," i.e., the hypothetical scenario is that had subjects not discontinued DB study drug, their efficacy would have been similar to the efficacy of subjects from the same treatment group and randomization stratum who did not discontinue DB study drug. All observed values of the endpoint of interest are excluded after DB study drug discontinuation (see Section 7.2), and statistical methods are used to estimate the treatment effect that would have been seen had the intercurrent event not occurred.

- For efficacy objectives assessed with a binary endpoint during the DBT Phase, DB study drug discontinuation is handled with a "composite strategy," i.e., the occurrence of the intercurrent event is integrated as a component of the endpoint. All observed values of the endpoint of interest are excluded after DB study drug discontinuation (see Section 7.2), and subjects with missing data are considered failures.
- For safety objectives, study drug discontinuation is handled with a "while-on-treatment strategy". All observed values of the endpoint of interest are used on or before study drug discontinuation + 7 days (see Section 7.2 and the Core SAP).
- For outcomes research and other objectives, study drug discontinuation is handled with a "treatment policy strategy", i.e., the occurrence of the intercurrent event is considered irrelevant, such that all observed values of the endpoint of interest are used regardless of study drug discontinuation.

Non-study prophylactic migraine medication use before the time point of interest defining the endpoint is also considered an intercurrent event. For all objectives, this intercurrent event is handled with a treatment policy strategy, such that all observed values of the endpoint of interest are used.

Nonstudy acute migraine-specific medication use before the time point of interest defining the endpoint is also considered an intercurrent event, except for efficacy objectives based on acute migraine-specific medication days or acute migraine medication days.

- For efficacy objectives based on migraine days, this intercurrent event is handled with a composite strategy, such that acute migraine-specific medication use is part of the endpoint definition of migraine days.
- For safety and outcomes research objectives, this intercurrent event is handled with a treatment policy strategy, such that all observed values of the endpoint of interest are used.

Use of nonstudy other medication to treat headache (migraine or nonmigraine) or aura before the time point of interest defining the endpoint is also considered an intercurrent event, except for the efficacy objective based on acute migraine medication days. For all objectives, this intercurrent event is handled with a treatment policy strategy, such that all observed values of the endpoint of interest are used.

See Section 4.1 for analysis sets that are used to assess endpoints.

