6.5 Early Discontinuation from the Study

Subjects MUST discontinue investigational product (and non-investigational product at the discretion of the investigator) for any of the following reasons:

- Withdrawal of informed consent (subject's decision to withdraw for any reason)
- Any clinical adverse event (AE), laboratory abnormality or intercurrent illness which, in the opinion of the investigator or sponsor, indicates that continued participation in the study is not in the best interest of the subject
- Pregnancy
- Termination of the study by Biohaven Pharmaceuticals
- Loss of ability to freely provide consent through imprisonment or involuntary incarceration for treatment of either a psychiatric or physical (e.g., infectious disease) illness

- Poor compliance with study procedures and visits, including poor completion compliance with evening reports in eDiary; poor compliance with study drug – see Schedule of Assessments Table 1 and Table 2.
- All subjects who discontinue in the DBT Phase early should comply with protocol specified DBT EOT procedures as outlined in Table 1. All subjects who discontinue in the OLE Phase early should comply with the protocol specified OLE EOT procedures as outlined in Table 2. The only exception to this requirement is when a subject withdraws consent for all study procedures or loses the ability to consent freely (i.e., is imprisoned or involuntarily incarcerated for the treatment of either a psychiatric or physical illness).

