9.1 Sample Size

With a sample size of approximately 480 randomized subjects per zavegepant treatment group and 240 randomized subjects per placebo treatment group, we expect approximately 440 subjects per zavegepant treatment group and 220 subjects per placebo treatment group in the migraine analysis set. Assuming zavegepant provides a 1-day advantage over placebo pooled on the mean change in migraine days per month over the entire DBT Phase (Weeks 1 to 12), and a common standard deviation of 4.2 days, then the study will have \geq 90% power for the primary endpoint with an alpha level of 0.025. The estimates for the migraine analysis set sample size, mean change in migraine days per month, and standard deviation are based on observed pooled data from rimegepant study BHV3000-305.

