## 5 SAMPLE SIZE, POWER, AND TYPE 1 ERROR

With a sample size of approximately 480 randomized subjects per zavegepant treatment group and 240 randomized subjects per placebo treatment group, we expect approximately 440 subjects per zavegepant treatment group and 220 subjects per placebo treatment group in the migraine analysis set. Assuming zavegepant provides a 1-day advantage over placebo pooled on the mean change in migraine days per month over the entire DBT Phase (Weeks 1 to 12), common standard deviation of 4.2 days, and a 2-sided  $\alpha = 0.025$  level, then the study has  $\geq 90\%$  power for the primary endpoint. The estimates for the migraine analysis set sample size, mean change in migraine days per month, and standard deviation (SD) are based on observed pooled data from rimegepant study BHV3000-305.

Type 1 error is not applicable. The significance of the primary and secondary endpoints will not be evaluated.

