# 6.3.2 Secondary Efficacy Endpoints

## 6.3.2.1 Percentages of Subjects with Reduction in Number of Migraine Days per Month

Analyses are based on the migraine analysis set using eDiary efficacy data dates in the OP and on-DBT efficacy analysis periods (see Section 7.2).

In analyses by months, subjects must (1) achieve the reduction criterion from OP in the number of migraine days per month in the specified month, (2) have  $\geq$  14 days of eDiary efficacy data (not necessarily consecutive) in the specified month, and (3) have  $\geq$  1 migraine day (absolute not prorated) of appropriate pain intensity in the OP analysis period to be classified as responders in the specified month. Otherwise, subjects are classified as failures in the specified month.

In analyses of the overall DBT, subjects must (1) achieve the reduction criterion from OP in the number of migraine days in the overall DBT, and (2) have  $\geq 1$  migraine day (absolute not prorated) of appropriate pain intensity in the OP analysis period to be classified as responders. Otherwise, subjects are classified as failures.

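### The missing-equals-failure rule has no exception for sponsor termination, so anyone it stopped between about day 14 and day 69 of the DBT Phase is a forced non-responder in Month 3, and in some cases Month 2

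*SAP*

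**What the plan says.** Protocol 6.5 lists the reasons for which study drug must be stopped. One of them is "Termination of the study by Biohaven Pharmaceuticals". SAP 1 reports that this happened: "Note that the study was terminated prematurely in December 2023 for business reasons and not a safety concern".

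SAP 3.2 (Intercurrent Events) states that "Study drug discontinuation before the time point of interest defining the endpoint is considered an intercurrent event" and does not separate reasons for stopping. For binary efficacy endpoints it applies a composite strategy: diary values after discontinuation are dropped and "subjects with missing data are considered failures". For continuous efficacy endpoints the same stop gets a hypothetical strategy.

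SAP 6.3.2.1 turns this into a monthly rule. A responder in a given month must meet the reduction criterion, have at least 14 diary days in that month, and have at least one migraine day in the Observation Phase. "Otherwise, subjects are classified as failures in the specified month". The denominator is the whole migraine analysis set. SAP 7.2 ends the diary window at the last double-blind dose, or the day before open-label dosing if that is earlier.

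The rule for response over the entire DBT Phase, in the same section, has no 14-day condition. Apart from the one response that supports secondary objective 1, all these responder results support exploratory objective 2.

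**The concern.** A composite strategy makes sense when stopping treatment says something about the treatment. A business decision by the sponsor does not: it cuts off observation for reasons unrelated to the subject. Counting the unobserved months as non-response treats administrative censoring as treatment failure.

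The plan is also uneven. For the same subject and the same stop, the continuous analysis treats the missing months as if treatment had continued, while the monthly responder table records failure. Both would appear in one report. SAP Version 8 was written because of the termination, and Version 9 reopened the intercurrent-event text to add two kinds of medication use, but neither addresses the termination itself.

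At stake are the Month 2 and Month 3 response rates and the differences from pooled placebo. If anyone was cut off mid-phase, these rates come out too low and, in expectation, the differences too small.

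**Working it through.** **The plan's own figure.** The only power statement concerns the primary endpoint: "Assuming zavegepant provides a 1-day advantage over placebo pooled", a "common standard deviation of 4.2 days, and a 2-sided" test at 0.025, about 440 subjects per dose and 2 × 220 = 440 on pooled placebo (SAP 5; Protocol 9.1 gives the same figures).

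- z = 1 / (4.2 × √(2/440)) = 1 / 0.2832 = 3.53
- power = Φ(3.53 − 2.24) = 0.9015

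This meets the stated "90% power for the primary endpoint with an alpha level of 0.025". It is a check on the inputs only. Neither document states a responder rate, so there is no responder figure to reproduce.

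**Which subjects the rule reaches.** Months are study days 1–28, 29–56 and 57–84 (SAP 6.3.1). Assume a complete diary up to the sponsor's stop, and count diary days per month against the 14-day rule.

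| Day of stop in DBT Phase | Month 1 | Month 2 | Month 3 |
|---|---|---|---|
| before 14 | not in migraine set | not in migraine set | not in migraine set |
| 14–41 | evaluable | forced failure | forced failure |
| 42–69 | evaluable | evaluable | forced failure |
| 70 or later | evaluable | evaluable | evaluable |

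The first row follows from SAP 4.1 and 6.3: a subject with no month of at least 14 diary days is excluded, not failed. Subjects who completed the DBT Phase and were stopped in the OLE Phase have a closed double-blind diary window and are untouched.

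**Effect on the estimate.** Let f be the share of the migraine set forced to fail in a month, equal in each arm and unrelated to response. Then

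- expected rate = p × (1 − f)
- expected difference = (p_zav − p_pbo) × (1 − f)

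With assumed rates of 40% and 30% (not in the documents):

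| f | Zavegepant | Placebo | Difference (points) |
|---|---|---|---|
| 0 | 40.0% | 30.0% | 10.0 |
| 5% | 38.0% | 28.5% | 9.5 |
| 10% | 36.0% | 27.0% | 9.0 |
| 20% | 32.0% | 24.0% | 8.0 |

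The factor (1 − f) is the same for any pair of rates. If the unobservable months leave the denominator, the expected difference stays at 10.0.

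**How large f might be.** The documents do not say. As an illustration, suppose entry was uniform over E weeks up to the stop. Entry days that lead to the migraine set number 7E − 14. Of these, 28 give a forced failure in Month 2 and 56 in Month 3.

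| E (weeks) | Month 2: 28/(7E − 14) | Month 3: 56/(7E − 14) |
|---|---|---|
| 52 | 28/350 = 8.0% | 56/350 = 16.0% |
| 104 | 28/714 = 3.9% | 56/714 = 7.8% |
| 150 | 28/1036 = 2.7% | 56/1036 = 5.4% |

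The documents bear on E. Protocol 4.3.3 says the OLE Phase was added after some subjects had entered follow-up, and SAP 2.4 dates the version that added it to 16 November 2021. Dosing therefore began before then. From that date to 1 December 2023 is 730 + 15 = 745 days, about 106 weeks. Under uniform entry to the end, the 104- and 150-week rows fit better than the 52-week row. Entry concentrated late would raise f; entry closed 12 weeks or more before the stop would make it zero.

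**Scale against precision.** At 440 per group and 40% versus 30%, the 97.5% half-width is 2.24 × √((0.24 + 0.21)/440) = 7.2 points. A loss of 0.5 to 2 points is a bias well inside that width.

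**The case against.** The strongest objection is that nobody is shown to be affected. The SAP gives only the month of termination, and no section says that any subject was then in the 12-week DBT Phase. SAP Version 8 did replace the staged database locks with a single final one. That fits an unfinished DBT Phase, but it fits equally well a finished phase whose first lock had not yet been done. This stands, and it makes the point conditional.

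The consequence is also limited. The affected results are exploratory, SAP 5 says significance will not be evaluated, and the primary and other continuous efficacy endpoints use a hypothetical strategy. SAP 6.2.3.3 already tabulates reasons for not completing the DBT Phase, and 6.3.1.1 counts subjects with enough diary data in each month. All of this is true. However, neither table corrects the published response rates or shows how many failures are due to termination alone.

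A reader might infer more than the documents support:

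- **That every subject stopped in December 2023 becomes a non-responder.** Subjects who completed the DBT Phase and were in the OLE Phase do not, and those stopped before 14 diary days leave the migraine set.
- **That Month 1 is biased.** A subject in the migraine set with too few Month 1 diary days fails Month 1 through diary gaps, not through termination.
- **That secondary objective 1 is biased the same way.** Table 2 of the SAP assigns it the composite strategy, but the operative overall-DBT rule has no minimum number of diary days. A truncated subject is judged on the days observed and can be a responder. That mismatch is a separate point.
- **That the difference must shrink.** The factor (1 − f) is an expectation under equal f. With 4% cut off on active and 6% on placebo, 0.40 × 0.96 − 0.30 × 0.94 = 10.2 points. Concurrent allocation in blocks of 12 (SAP 2.2) makes near-equal shares likely but does not guarantee them.

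**Conclusion.** The gap in the rule is real. As written, a subject stopped by the sponsor on about days 14–41 of the DBT Phase is a forced non-responder in Months 2 and 3, and one stopped on about days 42–69 in Month 3. Expected rates and differences in those months are multiplied by (1 − f).

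Under uniform entry over 104 weeks or more, f would be at most about 4% in Month 2 and 8% in Month 3. An assumed 10-point difference would then become about 9.6 and 9.2. This rests on a complete diary, equal cut-off across arms and assumed response rates. The documents do not establish that f exceeds zero, so they do not support saying that the reported rates are in fact biased. They support saying that the plan prescribes the wrong handling if anyone was cut off mid-phase. The reach is confined to the Month 2 and Month 3 responder results under exploratory objective 2. It is worth correcting because the correction is cheap, not because it threatens the main conclusions.

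**What to change.** Make the change before the LSLV lock, while draft outputs still use dummy treatment groups (SAP 2.3).

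- In SAP 3.2, state that discontinuation due to sponsor termination is administrative censoring and not a composite failure.
- In SAP 6.3.2.1, restrict the Month 2 and Month 3 denominators to subjects whose first dose was early enough to allow at least 14 diary days in that month before the sponsor's stop date: at least 42 days of possible treatment for Month 2 and 70 for Month 3, counting the first dose as day 1. Eligibility then depends on the date of first dose and not on what happened afterwards, and it matches the plan's own evaluability rule. Requiring the whole month (56 or 84 days) would drop subjects the SAP treats as evaluable, namely those stopped on days 42–55 for Month 2 and 70–83 for Month 3.
- Keep the failure rule for every other reason.
- Report results on both denominators, and the number of termination-only failures by arm and month.

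The cost is some SAP wording, one date filter and a smaller N in Months 2 and 3. If 10% were removed, 396 per group would remain, and the half-width at 40% versus 30% would go from 7.2 to 2.24 × √(0.45/396) = 7.6 points. The sponsor's stop date must be written down, since the documents give only a month and do not show that all subjects stopped on one day. If nobody was in the DBT Phase at termination, the results do not change.
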